***Infanrix hexa and Prevenar 13 Information sheets will be provided by TN to the participating carers.***

➤ Immunisation to be given by same medical doctor and investigator TN for all participants.

3) Supply of supplements for 4 weeks – and discussion of administration

Supply of diary: Daily 7pm temperature, infant sleep/cry

### **Visit 3 – week 8 – final visit**

1) **Assessments:** Weight, growth, temperature, other symptoms, collection of infant home diary and carer sleep diary; Carer: Mood Q; Tolerability & compliance Q  
& Blinding

### **Sample size & Justification**

A sample size of **50 participants:** Active group: Vit D + probiotic (n=25); Placebo group (n=25) suggested for this pilot study to obtain baseline values and variance for a larger study.

### **Analysis**

Analyses will be performed using SPSS (PASW version 18). Statistical significance will be set at  $p < 0.05$ . Between-group differences will be analysed by ANOVA comparing data after vaccination at 4 weeks (mean of daily data 4-8 weeks incl temperature, sleep/cry, carer sleep; or infant weight/growth data or carer mood data at 8 weeks) to data before vaccination (mean of daily data 0-4 weeks; or at 0 and 4 weeks).

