### **Intervention/ Comparison**

Sample size: n=50

Active group: n=25

Placebo group: n=25

**Active group:** 1000 IU Vitamin D & 2.3g Probiotics daily for 2 months

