**TIME LINE**

**Appointments with doctor:**

**Outcome measures**

| Primary (1), Secondary (2) | Outcome measures         | Tests        | Equipment                         | Lab/ location | Time points              |
|----------------------------|--------------------------|--------------|-----------------------------------|---------------|--------------------------|
| 1                          | Tympanic ear temperature | Temp         | Thermometer                       | NIIM, home    | Daily incl 0, 4, 8 weeks |
| 1                          | Weight, Growth           | scales       | Growth chart, weight chart        | NIIM          | 0,4,8 weeks              |
| 2                          | Sleep / cry              | Q/ diary     | Daily diary for infant collection | NIIM, home    | Daily                    |
| 2                          | Other symptoms           | Q            | Colds, mouth ulcers, rashes       | NIIM, home    | 0,4,8 weeks              |
| 2                          | Mood/ Stress             | Bond Lader Q | Main carer                        | NIIM          | 0,4,8 weeks              |
| 2                          | Sleep                    | Q            | Main carer                        | home          | Daily                    |

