### **Growth: Weight and size**

For size and weight measurements, standard scales will be use available at the clinic at all appointments.

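### Several unranked primary measures are each tested at an unadjusted 0.05 in a pilot whose sample size is justified only by estimation

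*Protocol*

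**What the plan says.** Four parts of the protocol bear on this.

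- **Outcome measures (table).** Two rows carry the primary label: "Tympanic ear temperature" and "Weight, Growth". Neither is placed above the other.
- **Growth: Weight and size.** Weight and size are distinct measurements: "For size and weight measurements, standard scales will be use". The second primary row therefore holds at least two variables, which makes at least three with temperature.
- **Sample size & Justification.** The 25 + 25 infants are "suggested for this pilot study to obtain baseline values and variance for a larger study". No effect size, SD, power or dropout rate is given.
- **Analysis.** "Between-group differences will be analysed by ANOVA", and one level is set for all of it ("Statistical significance will be set at" p < 0.05): temperature, weight/growth, infant sleep/cry, carer sleep and carer mood. For measures taken only at visits, the pre-vaccination reference is "or at 0 and 4 weeks". The section does not adjust the level, rank the primaries, say how they combine, or call the tests exploratory.

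**The concern.** A pilot that exists to supply planning values needs estimates and their precision. The Analysis section instead specifies a significance test at the conventional confirmatory level and applies it alike to every primary measure. The title and the Study Design section describe the trial as investigating the effect of supplementation, so a p-value below 0.05 on any primary measure could easily be written up as an effect.

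Two things are at stake. First, with several unranked primaries, a claim resting on whichever one crosses 0.05 carries more than a 5% risk of being false. Second, the quantities the larger study would be built on, the difference between arms and the SD, each with its uncertainty, are not named as outputs in the section that governs the analysis.

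**Working it through.** **Inputs from the protocol**

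- Per-test level 0.05 (Analysis). Sidedness is not stated; with two groups the ANOVA F test is non-directional, so it is treated as two-sided.
- Number of primary tests k: 2 if each primary row counts as one test, 3 if weight and size are tested separately (Outcome measures; Growth: Weight and size).
- n = 25 per arm, 50 in total (Intervention/ Comparison; Sample size & Justification). Only the sum 25 + 25 = 50 can be reproduced, because no power inputs are stated.

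**Assumptions not in the protocol**

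- Any one significant primary measure is reported as an effect.
- The correlations between test statistics are as given below. The protocol gives none, so a range is shown.

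**Step 1. Independent tests, no true effect on any measure**

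P(at least one p < 0.05) = 1 − (1 − 0.05)^k

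- k = 2: 1 − 0.95² = 1 − 0.9025 = 0.0975, or 9.75%
- k = 3: 1 − 0.95³ = 1 − 0.857375 = 0.1426, or 14.3%

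Whatever the correlation, the rate cannot exceed k × 0.05: 10% for two tests and 15% for three.

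**Step 2. Correlated tests**

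These are simulated rates from 2 million draws of two-sided normal test statistics.

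| Assumed correlation | Two tests, correlated | Three tests, only weight and size correlated | Three tests, all equally correlated |
|---|---|---|---|
| 0.5 | 9.1% | 13.7% | 12.5% |
| 0.7 | 8.3% | 12.9% | 10.9% |
| 0.9 | 7.0% | 11.7% | 8.4% |

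Correlation lowers the rate, so the independence figures are not a floor. Every cell is still above 5%.

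**Step 3. What 25 per arm can deliver as estimates (full follow-up, 48 degrees of freedom)**

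- Half-width of the 95% confidence interval for an arm difference: t(0.975, 48) × √(2/25) = 2.011 × 0.283 = 0.57 SD.
- 95% confidence limits for the pooled SD, as multiples of the estimate: √(48/69.02) = 0.83 and √(48/30.75) = 1.25.
- A required sample size is proportional to the variance, so one built on that SD could be off by a factor of 48/69.02 = 0.70 to 48/30.75 = 1.56.

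Step 3 is not an error in the plan; any study with 25 per arm has this precision. It shows why the intervals should be reported next to the estimates when the larger study is sized.

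**Step 4. Rate after adjustment, if testing is kept**

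An equal split of 0.05 gives, under independence, 1 − 0.975² = 4.94% for two tests and 1 − (1 − 0.05/3)³ = 4.92% for three. Holm also holds the overall rate at or below 5%, under any correlation, and is never less powerful than the equal split.

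**The case against.** The strongest reply is that this is largely a matter of silence. Multiplicity, the combination of primaries, confidence intervals and exploratory labels are commonly left to a statistical analysis plan, which may exist and is not at hand. A pilot may estimate variance and also print p-values, and ANOVA yields group means and a residual variance as by-products. That much stands: the absence of a multiplicity section would not by itself be a finding. The reply does not dispose of the point, because the number of primary measures, the unqualified level and the purpose of the sample size are all fixed in the protocol, and they do not agree with one another.

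Three stronger readings are tempting, and the document does not support them.

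- **That any significant primary counts as success.** The protocol states a level and a test, not a combining rule. If all primaries had to be significant, the false-positive rate would not be inflated. The figures above are therefore conditional.
- **That p ≥ 0.05 will be taken to show no effect.** Nothing in the protocol says so.
- **That each growth measure is tested twice, once against week 0 and once against week 4.** "or at 0 and 4 weeks" can equally mean one repeated-measures analysis or one combined reference, so counting extra tests would rest on an assumed reading.

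It is also fair to say that growth stands in the trial's title, so making it secondary would change an objective. The documents do not require that.

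**Conclusion.** The point holds as a mismatch between stated sections: at least three unranked primary measures, an unadjusted 0.05 for each, and a sample size of 50 justified only by what a later trial needs to know.

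Its size depends on how results are claimed. If one significant primary is enough to report an effect, the false-positive chance is roughly double to nearly triple the nominal 5% under independence. For three measures it stays more than twice 5% when only weight and size are correlated within the assumed range. It is smaller when all measures are correlated, and nil if all primaries must be significant. This is worth correcting before analysis, but it does not undermine the design.

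**What to change.** In the Analysis section:

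1. State that the main output for each outcome is the difference between arms with its 95% confidence interval, together with the pooled SD and its 95% confidence interval, for use in sizing the larger study.
2. Label all p-values exploratory.
3. If a confirmatory claim on the primary outcomes is to be kept, do one of two things. Either name a single primary measure in the outcome table; the introductory statement of the project's aim singles out daily temperature, which makes it the natural candidate. Or keep all the primary measures, list them explicitly, and apply Holm across them at an overall 0.05. With three measures, the smallest p-value is then compared with 0.05/3 = 0.0167, the next with 0.025 and the last with 0.05, stopping at the first that fails.

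Items 1 and 2 change wording only. They need no extra infants, visits or data, and growth can stay primary. The cost is that a nominal p < 0.05 on a single measure can no longer be claimed as a confirmed effect. Under item 3, naming one primary measure gives up primary status for the others, and Holm costs some power on each measure.

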## **STUDY DESIGN**

Randomised parallel double-blind placebo-controlled trial of 2 months duration investigating the effect of supplementation with vitamin D and probiotics on behavioural and physiological response in infants during routine childhood immunisation.

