#### **Enrolment & randomisation**

The doctor and chief investigator TN will meet patients at the NIIM clinic to confirm eligibility and to collect the infant's care givers informed consent. Two groups will be recruited into this pilot study, group 1: vaccination-naïve (not yet immunised) infants 4-24 months into the study, and group 2: vaccinated infants 4-24 months.

Eligible infants will be enrolled and randomised. A computer-generated permuted block randomisation schedule prepared by a researcher not involved in patient recruitment and data collection will be used to allocate patients to the active or placebo groups.

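### The analysis sentence leaves the before/after model open, sets two before readings against one after reading for growth and mood, and should name a baseline-adjusted, one-row-per-infant analysis

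*Protocol*

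**What the plan says.** The Study Design section describes a "Randomised parallel double-blind placebo-controlled trial of 2 months duration", and under Enrolment & randomisation the infant is the unit allocated: "Eligible infants will be enrolled and randomised". The outcome table lists two primary outcomes: ear temperature, recorded "Daily incl 0, 4, 8 weeks", and weight/growth, measured at weeks 0, 4 and 8. Carer mood, a secondary outcome, is also taken at weeks 0, 4 and 8.

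The Analysis section is short. It fixes the software, the significance level and one method for all outcomes: "Between-group differences will be analysed by ANOVA comparing data after vaccination at 4 weeks". The after data are "mean of daily data 4-8 weeks incl temperature, sleep/cry, carer sleep; or infant weight/growth data or carer mood data at 8 weeks". These are compared "to data before vaccination (mean of daily data 0-4 weeks; or at 0 and 4 weeks".

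Supplements are handed out at Visit 1 (week 0), and vaccination is at Visit 2 (week 4). The section on sample size justifies 50 infants (25 per arm) as a pilot meant to supply baseline values and variance for a larger study.

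**The concern.** Two features of the analysis sentence cause difficulty.

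**The comparison is not determined for weight/growth and carer mood.** There are two before readings and one after reading. The analyst could use week 0, week 4, their average, or all three readings as separate records. These choices do not estimate the same thing, because by week 4 the active arm has had four weeks of supplement.

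**The ANOVA model is unqualified.** Before and after values come from the same infant, so they are correlated. The sentence mentions no subject term, change score or baseline covariate. One model that the wording permits, an unpaired arm-by-period ANOVA, would use the wrong error term.

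At stake are the test on one primary outcome and the usefulness of the variance estimates, which are the pilot's stated purpose. The residual of an unpaired model is not the variance needed to plan a before/after comparison.

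**Working it through.** **Inputs.** From the protocol: 25 infants per arm and significance at 0.05 (two-sided assumed). The protocol gives no SD, effect size or correlation, so there is no figure of its own to reproduce. Assumed: SD 1 at each time, equal correlation ρ between times, ρ = 0.5 with range 0.3 to 0.9.

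**1. Which before reading?** Let the supplement effect on weight or mood be δ at week 8 and fδ at week 4, with f unknown (0 to 1). The between-arm difference in change then estimates:
- week 8 minus week 0: δ
- week 8 minus the average of weeks 0 and 4: δ − fδ/2 = (1 − f/2)δ
- week 8 minus week 4: (1 − f)δ

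At f = 0.5 these are δ, 0.75δ and 0.5δ. At f = 1 they are δ, 0.5δ and 0. Only week 0 precedes supplementation.

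**2. Precision of the valid options** (variance per infant):
- change from week 0: 2(1 − ρ)
- ANCOVA on week 0: 1 − ρ²
- ratio of ANCOVA to change: (1 + ρ)/2

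| ρ | change | ANCOVA | reduction |
|---|---|---|---|
| 0.3 | 1.40 | 0.91 | 35% |
| 0.5 | 1.00 | 0.75 | 25% |
| 0.7 | 0.60 | 0.51 | 15% |
| 0.9 | 0.20 | 0.19 | 5% |

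Change from the average of weeks 0 and 4 has variance 1.5(1 − ρ). That is 0.75 at ρ = 0.5, equal to ANCOVA, and smaller than ANCOVA above that. So the case for week 0 over the two-reading average rests on what is estimated (step 1), not on precision.

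**3. If an unpaired arm-by-period ANOVA were run** (one before and one after value per infant, 100 records, error df 96):
- Arm-by-period contrast: true variance is (1 − ρ) times the variance assumed. At ρ = 0.5, type I error is P(|Z| > 1.96/√0.5) = P(|Z| > 2.77) = 0.6%.
- Its standard error is too large by 1/√(1 − ρ), which is 1.41 at ρ = 0.5.
- Arm main effect: true variance is (1 + ρ) times that assumed. At ρ = 0.5, type I error is P(|Z| > 1.96/√1.5) = P(|Z| > 1.60) = 11%.
- Power at ρ = 0.5: the paired standard error is √(4 × 0.5/25) = 0.283, and 80% power needs an effect of 0.81 SD. The unpaired test uses √(4/25) = 0.40, so its statistic centres on 0.81/0.40 = 2.02 with spread √0.5 = 0.71, against a critical value of 1.985. Power is about 52%.

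Simulation agrees:

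| ρ | arm-by-period type I error | power (paired = 80%) | arm main effect type I error |
|---|---|---|---|
| 0.3 | 2% | 69% | 8% |
| 0.5 | 0.6% | 52% | 11% |
| 0.7 | 0.06% | 24% | 13% |
| 0.9 | about 0 | under 1% | 15% |

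**4. If a change-score or two-period repeated-measures ANOVA is run**, simulated type I error is 5.0% to 5.1% at every ρ from 0 to 0.95.

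**The case against.** A reader might infer that the protocol prescribes an ordinary ANOVA that treats paired values as independent, and so gives wrong p-values and intervals for both primary outcomes. The document does not support that. It says ANOVA without qualification, and repeated-measures ANOVA and ANOVA of within-infant change are both ANOVA. A between-group comparison of after with before, with daily readings first averaged, fits either of them naturally, and both hold their type I error. Nothing says that 100 or 150 values enter as independent records.

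Even under the unpaired reading, the contrast that matches the stated comparison would be conservative. Only the arm main effect would be significant too often. The pilot's variance estimates are not tied to an ANOVA residual either: the paired data are collected, so the SD of change can be computed whichever test is run. A statistical analysis plan, not shown here, may also settle the model.

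All of this stands, and it limits the point. Two things remain. The protocol itself fixes weeks 0 and 4 as the before data for growth and mood, and a paired reading does not say how two before values and one after value become one comparison. It also fixes a method without baseline adjustment, although week-0 values are collected at Visit 1 and would give a more precise analysis than a change from week 0.

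**Conclusion.** The point holds as a low-cost improvement, not as a demonstrated error in the test. For weight/growth and carer mood, the sentence determines no single per-infant comparison. Depending on how it is read, the estimate is the full week-8 effect, (1 − f/2) of it, or (1 − f) of it, where f is the unknown share already present at week 4. ANCOVA on week 0 removes that ambiguity and has 25% lower variance than a week-0 change score at ρ = 0.5 (35% at 0.3, 5% at 0.9).

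For the daily outcomes, including temperature, the wording is compatible with a valid analysis and needs only to say so. The losses from an unpaired model are conditional on that one reading. All figures rest on an assumed ρ, equal variances and equal correlation between times, since the protocol gives none of these.

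**What to change.** In the protocol's Analysis section:

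- **Weight, growth and carer mood:** ANCOVA of the week-8 value on arm, with the week-0 value as covariate, one row per infant (or carer).
- **Daily outcomes (temperature, infant sleep/cry, carer sleep):** compare arms on one after-minus-before value per infant, or use the arm-by-period term of a mixed model with infant as random effect. Describe this as the test of the before/after comparison already stated, not as the only test of the supplement, because both periods are on supplement.
- **For the larger study:** report the SD of within-infant change and the before/after correlation for each outcome.

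The cost is a few sentences, with no new data, visits or infants, and these are standard models. There are two small downsides. An infant missing week 0 or week 8 drops out of the ANCOVA, and week 4 no longer enters the reference for growth and mood, which gives up some noise reduction if ρ is above 0.5.

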### **Tympanic ear temperature**

Daily 7pm measurements using the Infrared Thermometer ET100B, available from Medshop Australia.

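### Averaging the daily temperature over the four weeks after vaccination dilutes a short vaccination reaction; a window of a few evenings tied to the actual vaccination date would serve that question better

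*Protocol*

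**What the plan says.** The table under Outcome measures marks two outcomes as primary: tympanic temperature and weight/growth. Temperature is taken "Daily incl 0, 4, 8 weeks", and the section on tympanic temperature specifies "Daily 7pm measurements using the Infrared Thermometer ET100B". Study Design gives the aim as the effect of supplementation on "behavioural and physiological response in infants during routine childhood immunisation".

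The only analysis given for temperature is in the Analysis section: "Between-group differences will be analysed by ANOVA comparing data after vaccination at 4 weeks". The post-vaccination value is the "mean of daily data 4-8 weeks incl temperature, sleep/cry, carer sleep" and the comparator is the "mean of daily data 0-4 weeks; or at 0 and 4 weeks". The significance level is 0.05. No shorter window, peak or count of fever days is named.

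Two other parts of the protocol bear on this. Both arms take their supplements in both four-week periods. The Visit 2 section postpones vaccination when an infant has had a fever in the preceding four weeks, and the Analysis section does not say whether the averaging windows then move with the vaccination. The sample of 50 is "suggested for this pilot study to obtain baseline values and variance for a larger study"; no power, effect size or SD is stated.

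**The concern.** Because supplements are taken before and after vaccination alike, an after-minus-before contrast cancels any steady supplement effect on temperature. What it mainly retains is the difference between arms in the response to vaccination. If that response lasts a few days, most of the 28 readings in the post-vaccination mean carry none of it. Sleep/cry is averaged in the same way.

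Two features could weaken the contrast further. The four weeks before vaccination are screened for fever and the four weeks after are not, so intercurrent illness adds variation mainly to the later mean. If vaccination is postponed while the windows stay tied to study weeks, the later mean would also include pre-vaccination days.

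At stake is how a non-significant result is read, and which outcome's variance is carried into the larger study.

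**Working it through.** **The plan's own figure.** There is none to reproduce, since the protocol gives no power, SD or expected effect.

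**From the protocol:** one reading a day; about 28 readings in each period; 25 infants per arm; significance level 0.05 (two-sided assumed). Every other input below is an assumption.

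**1. Dilution of the raw difference.** A reaction lasting k days is diluted 28/k-fold in the 28-day mean: 28/2 = 14, 28/3 = 9.3, 28/5 = 5.6.

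**2. Scenario A: a decaying reaction that varies between infants.** The placebo reaction is +0.8 °C on the vaccination evening and +0.4 °C on the next, halved in the active arm. Its size varies between infants (gamma, mean 1, shape 1.5, so variance 1/1.5 = 0.667). The day-to-day SD is 0.35 °C. An infant's stable level cancels in a change.
- Difference between arms: half of 1.2 is 0.6 degree-evenings. That gives 0.6/28 = 0.021 °C on the 28-day mean and 0.6/3 = 0.20 °C on a 3-evening mean.
- Variance of the 28-day change: 2 × 0.35²/28 + 0.667 × ½[(1.2/28)² + (0.6/28)²] = 0.00875 + 0.00077 = 0.0095, so SD 0.098 and standardised effect 0.021/0.098 = 0.22.
- Variance of the 3-evening mean minus the 28-day pre-vaccination mean: 0.35²/3 + 0.35²/28 + 0.667 × ½[0.4² + 0.2²] = 0.0408 + 0.0044 + 0.0667 = 0.112, so SD 0.334 and standardised effect 0.20/0.334 = 0.60.
- Loss in standardised effect: 0.60/0.22 = 2.7-fold, against a raw dilution of 9.3-fold.
- Simulated power: about 11% for the planned 28-day change and 56% for the 3-evening change.

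**3. Variations on scenario A.** Reactions ran from +0.5/+0.3 to +1.0/+0.5/+0.2 °C, the day-to-day SD from 0.2 to 0.5 °C, and the between-infant SD of true change from 0 to 0.1 °C. Power was 6 to 35% for the 28-day change and 24 to 76% for the 3-evening change. The short window was better in every case.

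**4. Scenario B: a constant difference D over k days.** Let sw be the day-to-day SD and sb the between-infant SD of true change.
- Planned change: difference D × k/28, SD √(sb² + 2sw²/28).
- Matched k-day window: difference D, SD √(sb² + sw²/k + sw²/28).
- Example with D = 0.5 °C, k = 3, sw = 0.4, sb = 0.1. The planned change has difference 0.5 × 3/28 = 0.054 °C and SD √(0.0100 + 0.0114) = 0.146, standardised effect 0.37, power about 0.25. The window has SD √(0.0100 + 0.0533 + 0.0057) = 0.263, standardised effect 1.90, power above 0.99. The ratio is 5.2.
- Over sw = 0.2 to 0.5 and sb = 0 to 0.3 °C, the loss in standardised effect is 4.1- to 8.8-fold for 3 days, 5.1- to 12.8-fold for 2 days and 3.1- to 5.4-fold for 5 days.

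| D over 3 days | Power, 28-day change | Power, 3-day window |
|---|---|---|
| 0.3 °C | 0.05 to 0.57 | 0.70 to >0.99 |
| 0.5 °C | 0.08 to 0.94 | at least 0.99 |

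The 0.94 occurs at sw = 0.2 and sb = 0. With sb of at least 0.1, the planned change reaches only 0.08 to 0.39 for D = 0.5 °C.

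**5. What the planned change could detect.** With 25 per arm, 80% power needs a standardised difference of about 0.79. At sw = 0.4 that is 0.085 °C (sb = 0) to 0.252 °C (sb = 0.3) on the 28-day mean, equivalent to an average difference of 0.79 to 2.36 °C over three days.

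**The case against.** A reader might infer from the dilution that the analysis loses sensitivity tenfold, or could not detect an effect at all. The documents do not support either. Raw dilution is not loss of detectability, because averaging 28 readings also shrinks the noise. The protocol gives no reaction length, effect size or SD, and with low noise or a large effect the 28-day change can reach high power. The 3-evening window is not well powered throughout either (24 to 76% in the scenario A variations), so sample size is part of the limitation.

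The acute reaction is also not the only stated aim. The protocol's title and introduction speak of the effect of eight weeks of supplementation and of temperature followed daily for two months. For that question a four-week mean is a coherent summary, and illness in weeks 4 to 8 may be part of an immune effect and not mere noise. This stands, and it is the reason to keep the 28-day mean.

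The trial is a pilot with no power claim. Since daily readings are collected, the variance of a shorter window can still be computed, so it would be too strong to say that the pilot can only yield the variance of an unsuitable endpoint. A statistical analysis plan not at hand may add windows. Weight/growth, the other primary outcome, is not affected.

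A reader might also object that antipyretic use is missing from the diary. The diary is described but not reproduced, so this cannot be checked and is not counted as an error.

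What remains is that the protocol does not leave the summary open. It fixes a 28-day mean as the only temperature analysis and attaches a significance test. A short window chosen after seeing the data would carry little weight.

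**Conclusion.** The point holds as a worthwhile, cheap improvement to the analysis of the vaccination response. It does not show that the temperature outcome is unusable. For an assumed reaction of 2 to 5 days, the raw difference is diluted about 6- to 14-fold. The loss in standardised effect is smaller: about 3-fold in scenario A, and about 4- to 9-fold for three days in scenario B. For modest short reactions the planned change probably has low power at 25 per arm. The short window did better in every case tried, but the size of the gain depends on assumed reaction length, effect and SDs.

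**What to change.** Before unblinding, prespecify as the temperature outcome for the vaccination response the mean (or maximum; choose one) of the 7pm readings on the actual vaccination evening and the next two evenings. Compare arms with adjustment for the pre-vaccination mean, or as change from it. State that the window follows the actual vaccination date when Visit 2 is postponed. Use the same window for sleep/cry. Keep the 28-day mean as a secondary summary of the broader eight-week supplementation effect, and report the variance of both summaries for the larger study.

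The cost is a few sentences of analysis text and no new measurements. The downside is that a three-reading summary is noisier per infant, more exposed to a missed evening, and could miss a later reaction. Recording any antipyretic given on those days is an optional addition.

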### **Participants**

#### **Inclusion criteria**

- Group 1 (preferred): Infants who have not yet been immunised (age range: 4-24 months).
- Group 2: Infants who have been immunised (age range: 4-24 months).
- Parents have agreed to have their child immunised.
- Normal infant growth as per WHO growth charts:  
<http://www.education.vic.gov.au/Documents/childhood/parents/mch/mchgrowthboy24mths.pdf>
- <http://www.education.vic.gov.au/Documents/childhood/parents/mch/mchgrowthgirl24mths.pdf>
- No tympanic temperature > 38 degrees Celsius in the preceding 4 weeks prior to immunisation
- Infants currently breastfed (e.g. exclusively or breast and formula fed)
- Infants currently not taking supplements (Vitamin D and/or probiotics)
- Infants who will remain in the same routine with primary carers for the 2 month study period
- Willing to contribute 50% (\$30) of the cost price for ear thermometer

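### Weight/growth, a primary outcome in infants aged 4-24 months, is analysed with no stated age or sex standardisation, which costs precision and inflates the variance the pilot is meant to supply

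*Protocol*

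**What the plan says.** - **Outcome.** The Outcome measures table ranks "Weight, Growth" as primary, alongside ear temperature, with measurements at weeks 0, 4 and 8. The equipment listed for it is "Growth chart, weight chart".
- **Measurement.** Under Growth: Weight and size: "For size and weight measurements, standard scales will be use available at the clinic at all appointments". No z-score, percentile or other derived variable is defined.
- **Population.** The Inclusion criteria admit "Infants who have not yet been immunised (age range: 4-24 months"), with the same age range for infants already immunised. Entry also requires "Normal infant growth as per WHO growth charts", with separate boys' and girls' charts linked.
- **Allocation.** Enrolment & randomisation describes permuted blocks and mentions no stratification by age or sex. There are 25 infants per arm.
- **Analysis.** Arms are compared by ANOVA at the 0.05 level. For this outcome, the post-vaccination data are "or infant weight/growth data or carer mood data at 8 weeks", compared "to data before vaccination (mean of daily data 0-4 weeks; or at 0 and 4 weeks"). No covariate is named.
- **Purpose.** Sample size & Justification presents the study as a pilot that supplies baseline values and variance for a larger trial.

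**The concern.** Infants near 4 months gain weight faster than infants near 24 months, and boys and girls follow different curves. The protocol accepts this at entry, where growth is judged on age- and sex-specific charts, but does not carry it into the stated comparison. Predictable differences in growth rate over a 20-month age span are therefore treated as random error.

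Two things are at stake. One of the two primary outcomes is estimated less precisely than the same data allow. In addition, the variance handed to the larger study includes age and sex variation that a better model would remove, so that study could be planned larger than it needs to be.

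**Working it through.** **Plan's own figure.** The 50 infants come with no effect size, SD or power, so there is nothing to reproduce. The documents also give no SD for weight or for weight gain. Every variance below is an assumption shown as a range.

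**Step 1: what the pre-post comparison already removes.** I read the ANOVA as a comparison of change from the infant's own earlier value. With pre-post correlation rho (assumed), SD of change / SD of raw value = sqrt(2(1 - rho)):
- rho 0.90: sqrt(0.20) = 0.45
- rho 0.95: sqrt(0.10) = 0.32
- rho 0.98: sqrt(0.04) = 0.20

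Most of the stable size difference between younger and older infants cancels. What remains is how the gain itself depends on age and sex.

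**Step 2: age-driven spread in the 8-week gain.** Assumptions: age uniform on 4-24 months, and 4-week gain = floor + (start - floor) x exp(-(age - 4)/6). The two cases are a start of 0.45 kg with a floor of 0.20 kg, and a start of 0.60 kg with a floor of 0.18 kg. Both give about 0.2 kg at 24 months.

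Let u = age - 4, uniform on 0-20:
- E[exp(-u/6)] = (6/20)(1 - exp(-20/6)) = 0.2893
- E[exp(-u/3)] = (3/20)(1 - exp(-20/3)) = 0.1498
- SD = sqrt(0.1498 - 0.2893²) = 0.257

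SD of 8-week gain from age = 2 x (start - floor) x 0.257:
- shallow curve: 2 x 0.25 x 0.257 = 0.129 kg
- steep curve: 2 x 0.42 x 0.257 = 0.216 kg

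Sex is not modelled here and would add to this.

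**Step 3: effect on precision.** Inflation of error variance = 1 + (age SD / residual SD)², and effective n per arm = 25 / inflation. With 25 per arm and two-sided alpha 0.05 (sidedness is not stated), the difference detectable with 80% power is (1.960 + 0.842) x sqrt(2/25) = 0.79 residual SD once age is removed. The last column is the unadjusted power for that same effect, Phi(2.802/sqrt(inflation) - 1.960).

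| Age SD (kg) | Residual SD (kg) | Inflation | Effective n per arm | Power |
|---|---|---|---|---|
| 0.129 | 0.4 | 1.10 | 22.7 | 76% |
| 0.216 | 0.4 | 1.29 | 19.4 | 69% |
| 0.129 | 0.2 | 1.41 | 17.7 | 65% |
| 0.216 | 0.2 | 2.17 | 11.5 | 48% |

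**Step 4: bias or only noise?** The SD of age is 20/sqrt(12) = 5.8 months. The standard error of the between-arm difference in mean age is 5.77 x sqrt(2/25) = 1.6 months, so a chance gap of up to 1.96 x 1.63 = 3.2 months is within the 95% range. Such gaps fall either way with equal probability. In 20,000 simulated null trials per setting, the unadjusted test rejected in 0.0479, 0.0485 and 0.0508 of trials when age explained 0%, 50% and 90% of outcome variance. The type I error is intact.

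**Step 5: consequence for the larger study.** For a fixed difference and power, sample size is proportional to error variance. Planning on the unadjusted variance would therefore make that study about 10% to 117% larger than an adjusted analysis needs, under the same assumptions.

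**The case against.** The strongest reply is that this is silence and not an error. Covariates and the scale of a derived outcome are often left to an SAP, and the SAP is not shown. That has force against any claim that the protocol forbids adjustment. It does not dispose of the point: the protocol names the test and the time points for a primary outcome, and a better analysis of the same data is available at almost no cost.

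Three stronger readings are tempting, and the documents do not support them.

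- **A reader might infer that raw kilograms and centimetres are analysed.** The text never says so. Growth and weight charts are listed as equipment for this very outcome. What can be said is that the analysis scale is undefined and no standardisation is stated.
- **A reader might infer that age noise overwhelms any supplement effect.** Infants are compared with their own earlier values, so only growth-rate variation remains. No effect size or SD is given, and under the mildest assumptions the detectable difference grows by only about 5% (sqrt(1.10) = 1.05).
- **A reader might infer that age imbalance would create a false growth effect.** Allocation is randomised, and the test already allows for chance imbalance. An age gap could cloud the reading of one result, but it is not systematic bias.

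It is also fair to say that a pilot makes no power claim, and that adjustment remains possible afterwards if age and sex are recorded. Both points lower the stakes for the test result. The pilot's purpose cuts the other way for the variance estimate, which is what the study exists to provide.

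**Conclusion.** The point holds as an inexpensive improvement to the analysis of a primary outcome. As written, age- and sex-dependent growth rate stays in the error term. This costs precision and inflates the variance intended for the larger study; it causes no systematic bias and no excess of false positives.

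The size is uncertain. Error variance is about 1.1 to 2.2 times larger, equivalent to 25 infants per arm acting like roughly 23 down to 12. That range rests wholly on assumed growth curves, a uniform age distribution and assumed residual SDs. The upper end needs the steepest curve together with the smallest residual SD. If most recruits fall in a narrow age band, the loss will be smaller. The better-supported consequence is the one for planning the larger study.

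**What to change.** In the Analysis section, define the growth outcome as WHO age- and sex-standardised weight and length z-scores, calculated at the infant's actual age at each visit. Compare week-8 z-scores between arms by ANCOVA with the week-0 z-score as covariate. Week 0 is the suitable baseline because supplements are supplied from that visit, so week-4 values already follow four weeks of allocated treatment. An alternative with the same purpose is ANCOVA of the week-8 measurement with baseline value, age and sex as covariates. Report the residual variance from the chosen model as the planning figure for the larger study, and show raw kg and cm descriptively.

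Two details need settling. The baseline data list does not name date of birth and sex, although the entry check on growth charts needs them, so they should be recorded explicitly. The reference used must also extend past 24 months, since an infant enrolled at that age will be nearly two months older at week 8.

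The cost is a look-up routine and a few lines of text, with no added visits, measurements or participants.
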